6.2.3. VISIT ASSESSMENTS

For by-visit summaries, nominal visits will be presented (i.e. visit windowing will not be applied). Unscheduled measurements will not be included in by-visit table summaries but will contribute to worst-case values table summaries. Listings will include both scheduled and unscheduled data.

7. STATISTICAL CONSIDERATIONS

Unless noted otherwise, the statistical considerations below will be applied. Data from all centers will be pooled for analyses.

- The issue of statistical multiplicity will not apply to this study.
- CIs will be presented as 2-sided 80% and 90% CIs, where noted in subsequent sections.

- Safety data will not be imputed except for incomplete dates associated with AEs and medications (rules in Appendix 1) and missing severity or relationship (rules in Section 17.1).
- Missing response data will be handled as described in Section 15.
- Summary statistics will include the number and percentage of patients in each category for discrete variables and the sample size, mean, median, standard deviation (SD), minimum, and maximum for continuous variables.
- When the denominator includes subjects with missing values, a “missing” category may be added for completeness and displayed last in the category summary.
- Time-to-event statistics will include the minimum, 25th percentile, median, 75th percentile, and maximum, provided they are estimable.
- All mean, median, and quartile values will be formatted to one more decimal place than the measured value. SD values will be formatted to two more decimal places than the measured value.
- The number and percentage of responses will be presented in the form xx (xx.x%) with percentage rounded to one decimal place.
- Change from baseline = post baseline value – baseline value
- Duration in days = end date – start date + 1 (divide by 7 to convert to weeks, divide by 30.44 to convert to months, and divide by 365.25 to convert to years; round result to 1 decimal place
- Listings typically will be sorted by study part, dose level / cohort, subject identification number (concatenated site and subject number), date, and time, if collected.

All analyses will be conducted using SAS version 9.4 or higher.

8. ANALYSIS POPULATIONS AND ENROLLMENT

The number of subjects in each analysis population (ITT, Safety, and DLT populations) will be summarized on the ITT population. Subjects in the ITT population but not in the S population will be counted in a ‘Not Treated’ column for table summaries on the Enrolled population. A subject listing indicating analysis population will be presented for the ITT population.

9. DISPOSITION

Subject disposition, including reasons for study withdrawal, will be summarized and listed based on the ITT population.

10. PROTOCOL DEVIATIONS

Protocol deviations will be summarized by major and minor category and by study part for the ITT population. All protocol deviations will be listed for the ITT population. Predefined categories of major protocol deviations include:

- Violation of inclusion/exclusion criteria
- Prohibited medications
- Study drug compliance

Additional categories may be added during the course of the study but will be determined prior to database lock.

11. DEMOGRAPHIC AND OTHER BASELINE CHARACTERISTICS

Demographic data and baseline characteristics will be summarized and listed for the ITT population. Demographics will include age (in years; descriptive statistics and by category: age <12, age \geq 12), sex, race, ethnicity, and baseline Karnofsky/Lansky performance status. Baseline disease characteristics will include tumor type, location of primary tumor at diagnosis, and tumor stage (0, I, II, III, IV, or unknown). Time (in months) from date of last disease progression until the informed consent date, inclusive, and time from initial disease diagnosis until the informed consent date will be summarized as continuous measures. Partial dates will be interpreted as July 1 when only a year is recorded and as the 15th of the month when only a month and year are recorded. If this interpretation yields a date of last progression or initial disease diagnosis after the informed consent date, then the partial date of last progression or initial disease diagnosis will be interpreted as January 1 when only a year is provided and the 1st of the month when only a month and year are provided. Other combinations of missing date elements will be handled as missing values.

Baseline tumor burden for subjects assessed under the RECIST 1.1 criteria will include descriptive statistics on the sum of target lesion diameters, number of target and non-target lesion, as well as presence of target lesions (yes/no), presence of lymph node target lesions (yes/no), and presence of non-target lesions (yes/no).

Baseline tumor burden for subjects assessed under the RANO criteria will include descriptive statistics for the sum of the product of target lesion diameters, the number of target lesions, the

number of non-target T1/Gd+ lesion and the number of T2/FLAIR lesions, as well as, presence of target lesions (yes/no), presence of non-target T1/Gd+ lesions (yes/no), presence of non-target T2/FLAIR lesions (yes/no).

12. PRIOR SURGICAL AND MEDICAL HISTORY

Surgical and medical history occurring prior to study treatment will be summarized and listed for the ITT population.

Verbatim terms will be coded using the Medical Dictionary for Regulatory Activities (MedDRA) version in effect at the time of the analysis. The number and percentage of subjects with any surgical and medical history will be summarized. Medical history will be summarized by MedDRA system organ class (SOC) and preferred term (PT).

Surgical history will be summarized by the MedDRA high-level group term (HLGT) and PT. Prior surgeries will be defined as surgeries performed on or prior to the date of first dose of study drug. Partial dates that cannot conclusively be identified as occurring after the start of treatment will be assumed to have occurred prior to start of treatment. Listings will include start date and stop date or notation of ongoing for conditions continuing into treatment.

13. MEDICATIONS AND PROCEDURES

Medications will be coded using World Health Organization (WHO) Drug Dictionary version in effect at the time of the analysis. For incidence summaries of medications by coded WHO Anatomical Therapeutic Chemical (ATC) category, a subject will be counted once per specific ATC category (likewise for preferred drug name).

13.1. PRIOR ANTI-CANCER THERAPY AND RADIOTHERAPY

Prior anti-cancer therapy and radiotherapy will be summarized and listed for the ITT population. The summary for prior anti-cancer therapies will include:

- Number of regimens (descriptive statistics and by category: 0, 1, 2, or more than 2 prior regimens)
- Number of regimens in the advanced/metastatic setting (0, 1, 2, or more than 2 prior regimens)
- Number of prior lines (descriptive statistics and by category: 0, 1, 2, 3, 4, or more than 4 prior lines)
- Therapy setting (Neoadjuvant, Adjuvant, Therapeutic for Advanced/Metastatic Disease, Consolidation, Maintenance, or Unknown); A subject may be counted in multiple

categories

- Incidence of prior anti-cancer therapies by WHO Drug ATC level 4 and preferred drug name
- Time from last PD to study entry
- Time for last anti-cancer treatment to study entry
- Best response

The summary for the prior radiotherapy will include:

- Number of prior courses (descriptive statistics and by category: 0, 1, or 2 or more courses)
- Sites of prior radiotherapy. A subject may be counted in multiple categories
- Type of radiation (total body irradiation, total marrow irradiation, proton therapy, radio surgery, gamma knife, other) by frequency.

Prior radiotherapy is defined as radiotherapy performed on or prior to the date of first dose of study drug. Partial dates that cannot conclusively be identified as occurring after the start of treatment will be assumed to have occurred prior to start of treatment.

13.2. PRIOR, CONCOMITANT AND POST-TREATMENT MEDICATIONS

Medications will be summarized and listed for the Safety population. Summary tables will include incidence (number and percentage) of subjects receiving any medication and incidence of specific medications by WHO Drug ATC level 4 and preferred drug name.

Prior, concomitant, and post-treatment medications will be summarized separately.

Categorization will be defined as follows:

- Prior medications will include medications which stopped prior to the first dose of study drug.
- Concomitant medications will include medications taken any time from the start of the first dose of study drug through 30 days following end of study drug administration or until the start of a subsequent anti-cancer therapy, whichever is earlier. Medications that started prior to the first dose of study drug but continued into treatment are considered as prior and concomitant.
- Post-treatment medications include medications which started more than 30 days after the end of study drug administration or after the start of a subsequent anti-cancer therapy,

whichever is earlier.

Appendix 1 provides additional detail for the interpretation of partial dates for medications.

13.3. CONCURRENT SURGERY AND PALLIATIVE RADIOTHERAPY

Concurrent anti-cancer surgery and palliative radiotherapy will be summarized for coded terms in the same manner as prior surgeries and prior radiotherapy. Concurrent anti-cancer surgery and palliative radiotherapy are those procedures that conclusively can be identified as occurring after the date of first dose of study drug up to, and including, the date of last dose of study drug.

13.4. POST-TREATMENT ANTI-CANCER THERAPY AND RADIOTHERAPY

Post-treatment anti-cancer therapies will include anti-cancer therapies which started after discontinuation of study drug. The number and percentage of subjects with post-treatment anti-cancer therapy noted during survival follow up, as well as the incidence (number and percentage) of anti-cancer therapies by WHO Drug ATC level 4 and preferred drug name will be summarized. Post-treatment anti-cancer therapy will be listed for ITT population. Post-treatment radiotherapy will be listed together with prior and concomitant radiotherapies for ITT population.

14. STUDY DRUG EXPOSURE AND COMPLIANCE

Study drug exposure and compliance will be summarized and listed by study part and overall, by dose level and cohort within the study parts for the Safety population. Listings will include details on dose interruption and/or dose modification.

14.1. STUDY DRUG EXPOSURE

The following summaries of study drug exposure will be presented:

- Duration of exposure (weeks) = [(last dose date of tazemetostat – first dose date of tazemetostat) + 1]/7. Except for the first and last dose dates, this calculation is not adjusted for periods where dosing is interrupted or dose is recorded as 0.
- Total number of cycles of study drug categorized as follows:
 - Cycle 1 (Days 1-28; weeks 1-4)
 - Cycle 2 (Days 29-56; weeks 5-8)
 - Cycle 3 (Days 57-84; weeks 9-12)
 - Cycle 4 (Days 85-112; weeks 13-16)
 - Cycle 5 (Days 113-140; weeks 17-20)
 - Cycle 6 (Days 141-168; weeks 21-24)
 - Cycle 7 (Days 169-196; weeks 25-28)

- Cycles 8 through 12 (Day 197-336; weeks 29-48); Note, cycles may be summarized individually if sufficient subjects are dosed at those cycles.
- Cycle 13 or more (Day 337 and beyond; week 49 and beyond); Likewise for Cycle 13 and beyond.
- Total amount of study drug taken (mg)
- For Cohorts 1 through 3: Average dose intensity (mg BID/day) = total amount of study drug taken (mg) / [2 * duration of exposure (days)]
- For Cohort 4: Average dose intensity (mg TID/day) = total amount of study drug taken (mg) / [3*duration of exposure (days)]
- Numbers of subjects requiring dose reductions, treatment interruption or treatment discontinuation in response to AEs (based on action taken for reported AEs)

14.2. STUDY DRUG COMPLIANCE

The following summaries of study drug compliance will be presented:

- Cohorts 1 through 3: Percentage study drug taken (summarized as a continuous variable) = $100\% * \text{Average dose intensity (mg BID/day)} / \text{assigned dose (mg BID/day)}$.
- Cohort 4: Percentage study drug taken (summarized as a continuous variable) = $100\% * \text{Average dose intensity (mg TID/day)} / 800 \text{ (mg TID/day)}$
- Category of percentage of study drug taken (using categories $\geq 90\%$, 80% to $< 90\%$, 70% to $< 80\%$, and $< 70\%$).

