5.3 Dosage and Administration

Tazemetostat must be dispensed or administered only to subjects enrolled in the study and in accordance with the protocol. Standard institutional procedures for administering an oral agent via by mouth will be followed. An adequate supply will be provided with instructions on home administration.

Tazemetostat administered to newly enrolled subjects: Based on benefit-risk assessment of the population studied in this clinical trial, following a report of CCI in a pediatric patient, from the time Amendment 7.0 approval to the completion of enrollment, the following doses will be the starting dose for new enrolled patients: For new patients with ATRT or any INI1-negative tumors with CNS involvement, the starting dose will remain 1200 mg/m² BID. For new patients that are non-ATRT, the starting dose will be 520 mg/m² BID. (See Section 6.5.3).

Tazemetostat administered as an oral suspension: The starting dose of tazemetostat (for dose escalation only) will be 240 mg/m²/dose given BID (based on free base) = 480 mg/m²/day. The amount of suspension per dose is calculated based on the subject's body surface area (BSA) and the assigned dose level. After the completion of Cycle 1, if a subject is unable to continue dosing with the oral suspension formulation due to adherence issues, the Medical Monitor should be contacted to discuss the possibility of switching to tablet dosing options.

Tazemetostat administered as a tablet (subjects in Cohort 4 only; Cohort 4 is closed to enrollment): Tazemetostat will be orally administered at the dose of 800 mg/m² TID (2400 mg/m²/day). Please see CCI for tablet dosing nomogram. This will provide instruction on the number of tablets to be taken based on BSA. After the completion of Cycle 1, if a subject is unable to continue dosing TID with the tablet formulation because of the quantity of tablets or schedule, the Medical Monitor should be contacted to discuss the possibility of switching to BID tablet dosing or BID suspension dosing.

For subjects on the tazemetostat BID oral suspension schedule, doses should be administered as close to 12 hours apart as possible, but there should be no less than 8 hours between doses. For subjects on the TID tablet schedule, doses should be administered as close to 8 hours apart as possible, but there should be no less than 4 hours between doses. Doses may be taken with or without food.

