5.5 Accountability

The Investigator/designee will be responsible for taking an inventory of each shipment of tazemetostat received and comparing it with the accompanying shipment form. The Investigator/designee will verify the accuracy of the information on the form, sign and date it, and acknowledge the shipment receipt according to the instructions provided.

The Investigator/designee must keep accurate written records of all tazemetostat received from the Sponsor. Additionally, the Investigator/designee must keep accurate records of the tazemetostat dispensed to subjects enrolled in this study including the quantity of suspension/number of tablets, lot number, date dispensed, subject initials and identification number, dose administered, balance forward, and the initials of the person dispensing the IP. Based on the entries in the site accountability forms, it must be possible to reconcile IP delivered with that used and returned. All IP must be accounted for and all discrepancies investigated and documented appropriately.

Tazemetostat stock may not be removed from the investigative site where originally shipped without prior knowledge and consent of the Sponsor or its designee. When authorized, all applicable local, state, and national laws must be adhered to for the transfer.

At the end of the study, all unused tazemetostat will be destroyed by the investigative site or sent to a designated contractor for disposal on behalf of the Sponsor, per the instructions at that time. Any IP returned to the Sponsor-designated contractors must be counted and verified by site personnel and the Sponsor or its designee. All certificates of delivery/receipts and/or return forms must be signed prior to shipment. The IP for return must be packed in a tamper-evident manner to ensure integrity is maintained during return. All IP returned must be in accordance with local, state, and national laws and must first be authorized by the Sponsor prior to shipment.

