Abbreviations: AE = adverse event, ALT = alanine aminotransferase, AST = aspartate aminotransferase, BID = twice daily, β -hCG = beta-human chorionic gonadotropin, BP = blood pressure, BSA = body surface area, ^{18}F FDG-PET = positron emission tomography with fluorodeoxyglucose, C1D1= Cycle 1 Day 1, CR = complete response, CSF = cerebrospinal fluid, CT = computed tomography, DNA = deoxyribonucleic acid, ECG = electrocardiograms, hr = hour, HR = heart rate, IHC = immunohistochemistry, MRI = magnetic resonance imaging, MUGA = multigated acquisition, PGx = pharmacogenomics, PK = pharmacokinetic, PT = prothrombin time, PTT = partial thromboplastin time, RR = respiratory rate, SAE = serious adverse event.

- a. **Pre-study procedures** and tumor assessment must be performed within 14 days before first dose of tazemetostat.
- b. **Screening:** Screening Period extends from Day -14 to Day -1. Disease assessments, however, are encouraged to be done in this time frame but may be done up to 28 days prior to C1D1 if necessary.
- c. **Demographics:** Age at time of enrollment, gender, ethnicity and race will be recorded (as allowed).
- d. **Medical History/Current Medical Conditions:** General and disease-specific medical history including a history of past and current medical conditions, full detailed history of primary diagnosis of the subject's malignancy, including stage of disease at diagnosis and date, therapies and responses to prior antitumor therapies will be recorded at Screening.
- e. **BSA:** The determination of tazemetostat doses will be based on BSA (standard institutional formula is acceptable or may be calculated by central Sponsor system) calculated using the subject's current height and weight at the beginning of each treatment cycle. Institutional guidelines for adjusting dose to account for changes in body weight are permissible.
- f. **Vital Signs:** Blood pressure (BP), heart rate (HR), temperature (T) and respiratory rate (RR) will be measured after the subject has been sitting for 5 minutes at Screening and regular intervals during treatment.
- g. **Performance Status:** Performance status will be evaluated using either Lansky ([Appendix 1](#)) or Karnofsky criteria ([Appendix 2](#)) based on the subject's age. If ≤ 12 years of age, use Lansky criteria; if > 12 years of age, use Karnofsky Performance Status criteria.

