 - Epithelioid malignant peripheral nerve sheath tumor
 - Extraskelatal myxoid chondrosarcoma
 - Myoepithelial carcinoma
 - Renal medullary carcinoma
 - Chordoma (poorly differentiated or de-differentiated)
 - Other INI1-negative malignant tumors with Sponsor approval
- Cohort 4 – approximately 12 subjects with one of the tumor types defined in Cohorts 1 through 3 or synovial sarcoma with SS18-SSX rearrangement

Subjects enrolled in cohorts 1-3 will receive the RP2D of 1200 mg/m² BID of tazemetostat in oral suspension. Subjects enrolled in cohort 4 will initially receive 800 mg/m² TID (2400 mg/m²/day) of tazemetostat administered as tablets, with the possibility to switch to BID tablet dosing or suspension dosing in subsequent cycles if unable to comply with the TID schedule. Cohort 4 was added to evaluate the administration of the tazemetostat tablet formulation in pediatric subjects who can swallow tablets, which may be more palatable.

Escalation and Expansion

Subjects will discontinue study treatment at the time of disease progression, development of an unacceptable toxicity, withdrawal of consent by subject and/or parent, or after 2 years of cumulative dosing or termination of the study.

Subjects also will undergo medical history assessment, physical examinations (PEs); vital sign measurements; echocardiogram (ECHO); performance status (Lansky/Karnofsky) assessments, blood sample collection for hematology, chemistry, PK, and PD markers; electrocardiograms (ECGs); adverse event (AE) assessments; concomitant medication assessments; and pregnancy testing for females of childbearing potential.

The study duration is approximately 24 months for each subject. The duration of screening for each subject will be approximately 14 days. The subject accrual period is planned for approximately 15 months. The duration of treatment will vary for each subject. Subjects may receive tazemetostat for a cumulative maximum of 2 years. Subjects will be followed for safety for approximately 30 days after the last dose of tazemetostat. For subjects that discontinue dosing, participation will continue for survival follow-up and response for 2 years from first dose of tazemetostat.

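### SAP 14.2 scores Cohort 4 compliance against a fixed 800 mg although the dose is 800 mg/m², so the percentage is right only while a child's assigned total is 2400 mg/day

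*SAP*

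**What the plan says.** SAP 14.1 defines the numerator in absolute milligrams: "For Cohort 4: Average dose intensity (mg TID/day) = total amount of study drug taken (mg) / [3*duration of exposure (days")]. It contains no BSA term.

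SAP 14.2 turns this into a percentage by dividing by one constant for every child, "Average dose intensity (mg TID/day)} / 800", labelled mg TID/day. The line for Cohorts 1–3 in the same section divides instead by "assigned dose (mg BID/day"). The percentage is summarised as a continuous variable and in four bands: ≥90%, 80 to <90%, 70 to <80% and <70%.

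The dose itself is per m². SAP 3.1: "Subjects enrolled in cohort 4 will initially receive 800 mg/m² TID (2400 mg/m²/day) of tazemetostat administered as tablets". Protocol 5.1 gives the tablet strength as 200 mg. Protocol 5.3 refers to a dosing nomogram, redacted in the public copy, and says of it: "This will provide instruction on the number of tablets to be taken based on BSA".

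**The concern.** The 800 in the denominator is the mg/m² dose carrying a mg label, and neither document converts one to the other. Two children who each take every assigned tablet would get different compliance percentages solely because they were assigned different numbers of tablets.

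The error runs in both directions. A child assigned less than 2400 mg/day prints below 100% despite full adherence. A child assigned more prints above 100% at full adherence, and real under-dosing can land in the ≥90% band. Masked under-dosing is the more troublesome case, because a figure between 90% and 100% looks ordinary.

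**Working it through.** **Inputs**
- Cohort 4 dose: 800 mg/m² TID (Protocol 5.3, SAP 3.1).
- Tablet: 200 mg (Protocol 5.1).
- Intensity: total mg / (3 × days) (SAP 14.1).
- Compliance: 100 × intensity / 800 (SAP 14.2).
- Not available: BSA values and the nomogram's cut-points.

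**The plan's own figure.** 800 × 3 = 2400 mg/m²/day, which equals 1200 × 2 as Protocol 1.5.2.2 states. The dose arithmetic is right, and it confirms that the 800 is a per-m² quantity.

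**General result.** Let A be the assigned mg per day, a the share of the assigned mg actually taken, and D the days of exposure.
- Total taken = a × A × D
- Intensity = a × A × D / (3 × D) = a × A / 3
- Printed % = 100 × (a × A / 3) / 800 = 100 × a × A / 2400

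The printed value equals 100 × a only when A = 2400 mg/day.

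**By tablet count, equal TID doses.** With n tablets per dose, A = 600n, so printed % = 100 × a × n/4. The adherence that prints as 90% is 90 / (n/4).

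| Tablets per dose | Assigned mg/day | Full adherence prints as | True adherence printing as 90% |
|---|---|---|---|
| 3 | 1800 | 75% | 120% (more than assigned) |
| 4 | 2400 | 100% | 90% |
| 5 | 3000 | 125% | 72% |
| 6 | 3600 | 150% | 60% |
| 7 | 4200 | 175% | 51.4% |
| 8 | 4800 | 200% | 45% |

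**One subject through the full formula.** Six tablets TID for 84 days, all taken: 6 × 200 × 3 × 84 = 302,400 mg. Intensity is 302,400 / 252 = 1200 mg. Printed: 1200/800 = 150%. Against the assigned 1200 mg: 100%. At 70% adherence the total is 211,680 mg and the intensity 840 mg. That prints as 105% (≥90% band), while the true value is 70% (70 to <80% band).

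**Changes during treatment.** A switch to six tablets BID is 2 × 6 × 200 = 2400 mg/day, and 2400/3 = 800, so it still prints correctly. If the assigned amount became 600 mg TID, full adherence would print as 600/800 = 75%.

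**Link to body size (assumption).** If tablets are rounded to the nearest whole tablet, n tablets cover (n − 0.5)/4 to (n + 0.5)/4 m². That is 0.875–1.125 m² for four tablets and 1.375–1.625 m² for six. The results by tablet count do not need this assumption.

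**The case against.** **The mg label may be shorthand.** A programmer might divide the total by BSA first, and 800 mg/m² would then be a valid denominator. But SAP 14.1 and 14.2 label every quantity in mg, so someone following the text exactly gets the wrong value. If mg/m² was meant, the text still needs correcting.

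**The Cohorts 1–3 line is not a clean model.** This stands in part. The SAP does not define the assigned dose, and SAP 3.1 gives those cohorts' dose as 1200 mg/m² BID. That line works only if the assigned dose is read as the subject's own mg amount, so both lines need the definition.

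**The reach is very small.** This stands. Four children are reported to have received tablets, Cohort 4 is closed, and no decision rule uses the percentage. Values of 125–200% would also stand out in the listings; a masked value near 90% would not.

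**Stronger readings that the documents do not support:**
- *Only four tablets per dose is scored correctly.* The condition is 2400 mg/day. Six tablets BID meets it, and the redacted nomogram could split tablets unequally over the day.
- *The interval between a stop under Protocol 6.5.3 and a later rechallenge is a second error, because it counts against compliance.* SAP 14.1 discloses its convention: "this calculation is not adjusted for periods where dosing is interrupted or dose is recorded as 0". The interval falls under that rule, interruptions are listed, and no rechallenge is documented.
- *Major deviations would be misclassified.* SAP 10 names study drug compliance as a major-deviation category but does not tie it to this percentage.

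**Conclusion.** Wrong as written, and minor. The Cohort 4 percentage is true adherence multiplied by assigned mg per day / 2400. It and its band can be trusted only while a child's assigned total is 2400 mg/day. This follows from the printed formulas and units alone.

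How far the four children's figures would be off cannot be determined, because neither their BSA nor the nomogram is in the documents. The percentages by tablet count are exact for equal TID doses held constant over the exposure period. A reader should not infer that any actual child's under-dosing has been hidden; the documents show only that the formula allows it.

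The affected output is descriptive: Cohort 4 compliance values and bands, and any pooled compliance row that includes these subjects, since SAP 14 also summarises by study part and overall. Response rate, the 3-of-20 rule and adverse event incidences do not use this percentage.

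**What to change.** In SAP 14.2, replace the fixed 800 with the subject's assigned dose in mg. The simplest general form is:

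Compliance = 100% × total mg taken / total mg assigned over the exposure period,

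where assigned mg per day = assigned tablets per day × 200 mg, updated at each dose, schedule or formulation change. State that the assigned dose in the Cohorts 1–3 line likewise means the subject's assigned mg amount. Leave duration of exposure as SAP 14.1 defines it.

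Use the amount actually assigned, not 800 mg/m² × current BSA. Tablets are whole units, and Protocol Table 11, footnote e, adds: "Institutional guidelines for adjusting dose to account for changes in body weight are permissible". For example, a fully adherent child of 1.12 m² assigned four tablets per dose scores 800/800 = 100% on the assigned amount, but 800/(800 × 1.12) = 800/896 = 89.3% on the per-m² target.

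Check of the fix: six tablets per dose at 60% adherence gives 720/1200 = 60%, where the current formula prints 720/800 = 90%.

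Cost: SAP wording and programming. Total mg taken is already required by SAP 14.1, and dose modifications are already listed under SAP 14. Protocol 5.5 has sites record the "quantity of suspension/number of tablets" dispensed and the dose administered. The documents do not show that the assigned tablet count is held in the clinical database. If it is not, it would have to be retrieved from site records for the four subjects.
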